10.3.1.2. Objective Response Rate, DCR, CBR, and DoR

Other secondary efficacy endpoints will be defined as shown in [Table JPCG.11](#).

Table JPCG.11. Other Secondary Efficacy Endpoints

Endpoint	Definition
ORR	The proportion of patients with CR or PR according to RECIST v1.1
DCR	The proportion of patients with CR, PR, or SD according to RECIST v1.1
CBR	The proportion of patients with CR, PR, or SD ≥ 6 months according to RECIST v1.1
DoR	The time from the date of first evidence of a CR or PR to the date of objective progression or death from any cause, whichever is earlier

Abbreviations: CBR = clinical benefit rate; CR = complete response; DCR = disease control rate; DoR = duration of response; ORR = objective response rate; PD = progressive disease; PR = partial response; RECIST v 1.1 = Response Evaluation Criteria in Solid Tumors Version 1.1; SD = stable disease.

The objective response rate (ORR), disease control rate (DCR), and clinical benefit rate (CBR) of each treatment arm will be calculated using the ITT population. All rates will be compared between the 3 treatment arms based on a normal approximation for the difference between the rates.

The duration of response (DoR) time is defined only for responders (patients with a best response of complete response [CR] or partial response [PR]). A Kaplan-Meier analysis of DoR will be performed to estimate the DoR curve for each arm.

10.3.1.3. Overall Survival

Overall survival is defined as the time from randomization until death from any cause. If the patient is alive or lost to follow-up at the time of data analysis, OS data will be censored on the

last date the patient is known to be alive. The first OS analysis will be at the time of the PFS analysis. The final analysis of OS will occur 24 months after the last patient enters treatment.

Overall survival will be compared between treatment arms using a stratified log-rank test, stratified by the randomization strata. The corresponding hazard ratio (HR) between treatment arms will be estimated using a stratified Cox regression model (Cox 1972), stratified by the randomization strata. Overall survival curves, the median OS time, and survival rates at every 6 months up to 24 months for each treatment arm will be estimated using the Kaplan-Meier method (Kaplan and Meier 1958).

10.3.2. Safety Analyses

All patients who receive at least 1 dose of any study therapy will be evaluated for safety and toxicity.

The National Cancer Institute (NCI) Common Terminology Criteria for Adverse Events (CTCAE) v 4.0 will serve as the reference document for choosing appropriate terminology for, and grading the severity of, all AEs and other symptoms. For AEs without matching terminology within the NCI -CTCAE v 4.0 criteria, the investigator will be responsible for selecting the appropriate system organ class and assessing severity grade based on the intensity of the event.

Both the CTCAE code and the AE verbatim text will be mapped by Lilly or its designee to corresponding terminology within the Medical Dictionary for Regulatory Activities (MedDRA) Version 18.1 (or higher). Adverse events will be reported using a process which includes both CTCAE v4.0 and MedDRA:

- In CTCAE version 4.0, each CTCAE term is a MedDRA lower level term (LLT), except in the case where the CTCAE term is a MedDRA System Organ Class (SOC) followed by 'Other – specify'.
- The CTCAE v4.0 term reported by the investigator will be mapped to the MedDRA Preferred Term (PT) and SOC of the corresponding MedDRA LLT, unless the reported CTCAE term is 'Other – specify'.
- If the reported CTCAE term is 'Other – specify', the MedDRA LLT, PT, and SOC mapped from the verbatim AE term will be used.
- All listings and summaries will use the PT resulting from this process. The LLT will be used in the treatment-emergent computation.

The following safety analyses will be based on the safety population. Safety analyses will be conducted by treatment arm and will include summaries of the following:

- AEs, including severity and possible relationship to study drug
- SAEs, including possible relationship to study drug
- AEs leading to dose adjustments
- discontinuations from study treatment due to AEs or death
- treatment-emergent abnormal changes in laboratory values
- treatment-emergent abnormal changes in vital signs
- extent of exposure

10.3.3. Other Analyses

10.3.3.1. Patient Disposition

A detailed description of patient disposition will be provided, including a summary of the number and percentage of patients entered into the study, enrolled in the study, and treated as well as reasons for discontinuation from study treatment and reasons for discontinuation from study. A summary of all important protocol deviations will be provided.

10.3.3.2. Patient Characteristics

Patient characteristics at baseline will be summarized by treatment arm:

- Patient demographics
- Baseline disease characteristics
- Historical illnesses
- Prior anticancer therapy

Other patient characteristics will be summarized as deemed appropriate

10.3.3.3. Concomitant Therapy

A summary of prior and concomitant medications by treatment arm will be reported.

10.3.3.4. Poststudy-Treatment-Discontinuation Therapy

The numbers and percentages of patients receiving poststudy-treatment-discontinuation anticancer therapies will be provided by type of therapy (surgery, radiotherapy, or systemic therapy), and by drug class and/or name, overall and by line of therapy.

10.3.3.5. Treatment Compliance

The number of cycles received, dose omissions, dose reductions, dose intensity, and treatment compliance will be summarized for all treated patients by treatment arm.

The actual cumulative dose taken will be determined based on counting the number of capsules returned at each visit and subtracting that number from the number of capsules dispensed. The expected cumulative dose to be taken will be determined based on the assigned dose and taking into account any dose reductions or omissions. Treatment compliance will be measured as a percentage of the actual cumulative dose divided by the expected cumulative dose.

10.3.3.6. Pharmacokinetic/Pharmacodynamic Analyses

PK analyses will be conducted on all patients who have received at least 1 dose of abemaciclib and have evaluable PK samples and sufficient dosing information.

Mean population PK parameters for abemaciclib in plasma (for example, clearance, exposure, volume of distribution,) and inter-individual PK variability will be computed using nonlinear mixed effect modelling (NONMEM).

Likewise, and if warranted by the data, mean population PK parameters for tamoxifen and endoxifen in plasma and interindividual variability estimates will also be computed using nonlinear mixed-effect modelling implemented in NONMEM.

The observed concentrations of abemaciclib, tamoxifen, and their respective metabolites may be summarized by time and dose.

PD samples will be collected as specified in the Study Schedule and PK and PD Sampling Schedule (cross reference). Refer to these attachments (including footnotes) for important information about these samples and their collection.

Furthermore, PD data (such as neutrophil, lymphocyte, or platelet counts in blood) collected in this study may also be analyzed by means of NONMEM and connected to the population PK model in a PK/PD model.

PD data from all patients undergoing PD assessments will be analyzed. The PD data will be combined and exploratory analyses will be conducted to determine if a relationship exists between plasma concentration and PD effect(s) in humans. Interpatient variability in human PD response may also be assessed.

10.3.3.7. Biomarker Analyses

Biomarker analyses will be based on the subset of patients from the above cohorts from whom a valid assay result (according to laboratory guideline) has been obtained. Exploratory correlative analyses will be performed to investigate associations between biomarkers and clinical endpoints as deemed appropriate.

10.3.3.8. Health Outcome/Quality of Life Analyses

Patient-reported outcomes are measured through paper versions of the following:

- mBPI-sf (modified Brief Pain Inventory, Short Form)
- EORTC QLQ-C30 (The European Organization for Research and Treatment of Cancer Quality of Life Questionnaire Core 30)

Descriptive statistics will be calculated for patient-reported data for each instrument.

Comparisons between arms will be made for pain, pain interference, functional scales (physical, role, emotional, cognitive, and social), other disease symptoms, health status, and overall quality of life. The number of missing and incomplete questionnaires/assessments by visit will be summarized for each instrument, including the reason not completed.

Exploratory analysis may be performed to investigate associations between patient-reported data (mBPI-sf and EORTC QLQ-C30) and additional clinical efficacy and/or utilization measures as appropriate.

Further analysis details will be described in the SAP.

10.3.3.9. Healthcare Resource Utilization

Utilization data overall and by study treatment arm will be summarized descriptively by category (for example, transfusions and hospitalization days) as appropriate.

Exploratory analyses may be performed to investigate associations between the utilization data and the clinical endpoints.

10.3.4. Subgroup Analyses

A prespecified list of subgroups will be identified in the SAP. The treatment effect within each subgroup will be summarized. Other subgroup analyses not specified in the SAP may be performed as deemed appropriate. These subgroups will be based on important characteristics, for example, prognostic significance.

Appendix 1. Abbreviations and Definitions

Term	Definition
AE	Adverse event: any untoward medical occurrence in a patient or clinical investigation patient administered a pharmaceutical product and that does not necessarily have a causal relationship with this treatment. An adverse event can therefore be any unfavorable and unintended sign (including an abnormal laboratory finding), symptom, or disease temporally associated with the use of a medicinal (investigational) product, whether or not related to the medicinal (investigational) product.
ALT	alanine aminotransferase
ANC	absolute neutrophil count
ASCO	American Society of Clinical Oncology
AST	aspartate aminotransferase
blinding	A procedure in which one or more parties to the trial are kept unaware of the treatment assignment.
CAP	College of American Pathologists
CBR	clinical benefit rate
CDK	cyclin-dependent kinase
CI	confidence interval
CIOMS	Council for International Organizations of Medical Sciences
collection database	a computer database where clinical trial data are entered and validated.
CR	complete response
CRP	Clinical research physician: Individual responsible for the medical conduct of the study. Responsibilities of the CRP may be performed by a physician, clinical research scientist, global safety physician, or other medical officer.
CT	computed tomography
CTCAE	Common Terminology Criteria for Adverse Events
DCR	disease control rate
DoR	duration of response
ECG	electrocardiogram
eCRF	electronic case report form
enroll	The act of assigning a patient to a treatment. Patients who are enrolled in the trial are those who have been assigned to a treatment.
enter	Patients entered into a trial are those who sign the informed consent form directly or through their legally acceptable representatives.

EORTC QLQ-C30	European Organization for Research and Treatment of Cancer Quality of Life Questionnaire-Core 30
ER	estrogen receptor
ERB/IRB	ethical review board/institutional review board
GCP	good clinical practice
HER2-	human epidermal growth factor receptor 2 negative
HIV	human immunodeficiency virus
HR	hazard ratio
HR+	hormone receptor positive
IB	investigator's brochure
ICF	informed consent form
ICH	International Conference on Harmonisation
IHC	immunohistochemistry
informed consent	A process by which a patient voluntarily confirms his or her willingness to participate in a particular trial, after having been informed of all aspects of the trial that are relevant to the patient's decision to participate. Informed consent is documented by means of a written, signed, and dated informed consent form.
Interim analysis	An interim analysis is an analysis of clinical trial data conducted before the final reporting database is created/locked.
Investigational product	A pharmaceutical form of an active ingredient or placebo being tested or used as a reference in a clinical trial, including products already on the market when used or assembled (formulated or packaged) in a way different from the authorized form, or marketed products used for an unauthorized indication, or marketed products used to gain further information about the authorized form.
ITT	intention-to-treat: The principle that asserts that the effect of a treatment policy can be best assessed by evaluating on the basis of the intention to treat a patient (that is, the planned treatment regimen) rather than the actual treatment given. It has the consequence that patients allocated to a treatment group should be followed up, assessed, and analyzed as members of that group irrespective of their compliance to the planned course of treatment.
IVRS/IWRS	interactive voice-response system/interactive web-response system
LLT	lower level term
mBC	metastatic breast cancer
mBPI-sf	modified Brief Pain Inventory-short form

MedDRA	Medical Dictionary for Regulatory Activities
MRI	magnetic resonance imaging
NCI	National Cancer Institute
ORR	objective response rate
OS	overall survival
PD	pharmacodynamic
PET	positron emission tomography
PFS	progression-free survival
PK	pharmacokinetic
PR	partial response
PT	Preferred Term
Q12H	every 12 hours
QD	every day
randomize	the process of assigning patients to an experimental group on a random basis
RANK-L	receptor activator of nuclear factor kappa-B ligand
RECIST	Response Evaluation Criteria in Solid Tumors
reporting database	A point-in-time copy of the collection database. The final reporting database is used to produce the analyses and output reports for interim or final analyses of data.
re-screen	to screen a patient who was previously declared a screen failure for the same study
SAE	serious adverse event
SAP	statistical analysis plan
screen	The act of determining if an individual meets minimum requirements to become part of a pool of potential candidates for participation in a clinical study.
screen failure	patient who does not meet one or more criteria required for participation in a trial
SOC	System Organ Class
SUSARs	suspected unexpected serious adverse reactions
TEAE	Treatment-emergent adverse event: an untoward medical occurrence that emerges during a defined treatment period, having been absent pretreatment, or worsens relative to the pretreatment state, and does not necessarily have to have a causal relationship with this treatment.

TBL	total bilirubin
ULN	upper limit of normal
VTE	venous thromboembolic event
women of child bearing potential (WOCBP)	Fertile, following menarche and until becoming postmenopausal, unless permanently sterile. Permanent sterilization includes hysterectomy, bilateral salpingectomy, and bilateral oophorectomy.

Appendix 2. Study Governance, Regulatory, and Ethical Considerations

Informed Consent

The investigator is responsible for:

- ensuring that the patient understands the potential risks and benefits of participating in the study
- ensuring that informed consent is given by each patient or legal representative. This includes obtaining the appropriate signatures and dates on the ICF prior to the performance of any study procedures and prior to the administration of study treatment.
- answering any questions the patient may have throughout the study and sharing in a timely manner any new information that may be relevant to the patient's willingness to continue his or her participation in the trial.

Ethical Review

Documentation of ERB/IRB approval of the protocol and the ICF must be provided to Lilly before the study may begin at the investigative site(s). Lilly or its representatives must approve the ICF, including any changes made by the ERBs/IRBs, before it is used at the investigative site(s). All ICFs must be compliant with the ICH guideline on GCP.

The study site's ERBs/IRBs should be provided with the following:

- the current IB and updates during the course of the study
- the ICF
- relevant curricula vitae

Regulatory Considerations

This study will be conducted in accordance with:

- consensus ethics principles derived from international ethics guidelines, including the Declaration of Helsinki and Council for International Organizations of Medical Sciences (CIOMS) International Ethical Guidelines
- applicable ICH GCP Guidelines
- applicable laws and regulations.

Some obligations of Lilly may be assigned to a third-party organization.

Investigator Information

Licensed physicians specializing in oncology will participate as investigators in this clinical trial.

Protocol Signatures

Lilly's responsible medical officer will approve the protocol, confirming that, to the best of his or her knowledge, the protocol accurately describes the planned design and conduct of the study.

After reading the protocol, each principal investigator will sign the protocol signature page and send a copy of the signed page to a Lilly representative.

Final Report Signature

The investigator will sign the final clinical study report for this study, indicating agreement, to the best of his or her knowledge, with the analyses, results, and conclusions of the report.

The clinical study report coordinating investigator will sign the final clinical study report for this study, indicating agreement that, to the best of his or her knowledge, the report accurately describes the conduct and results of the study.

An investigator will be chosen by Lilly to serve as the clinical study report coordinating investigator. If this investigator is unable to fulfill this function, another investigator will be chosen by Lilly to serve as the clinical study report coordinating investigator.

The Lilly responsible medical officer and statistician will approve the final clinical study report for this study, confirming that, to the best of his or her knowledge, the report accurately describes the conduct and results of the study.

Data Quality Assurance

To ensure accurate, complete, and reliable data, Lilly or its representatives will do the following:

- provide instructional material to the study sites, as appropriate
- sponsor start-up training to instruct the investigators and study coordinators. This session will give instruction on the protocol, the completion of the CRFs, and study procedures.
- make periodic visits to the study site
- be available for consultation and stay in contact with the study site personnel by mail, telephone, and/or fax
- review and evaluate CRF data and use standard computer edits to detect errors in data collection
- conduct a quality review of the database

In addition, Lilly or its representatives will periodically check a sample of the patient data recorded against source documents at the study site. The study may be audited by Lilly or its representatives, and/or regulatory agencies at any time. Investigators will be given notice before an audit occurs.

The investigator will keep records of all original source data. This might include laboratory tests, medical records, and clinical notes. If requested, the investigator will provide Lilly, applicable regulatory agencies, and applicable ERBs/IRBs with direct access to original source documents.

Data Capture System

An electronic data capture system will be used in this study. The site maintains a separate source for the data entered by the site into Lilly provided electronic data capture system.

Case report form data will be encoded and stored in a clinical trial database. Data managed by a central vendor, such as laboratory test data, will be stored electronically in the central vendor's database system. Data will subsequently be transferred from the central vendor to the Lilly data warehouse.

Any data for which the paper documentation provided by the patient will serve as the source document will be identified and documented by each site in that site's study file. Paper documentation provided by the patient may include, for example, a paper diary to collect patient-reported outcome (PRO) measures (for example, MDASI) or a participant diary.

Data from complaint forms submitted to Lilly will be encoded and stored in the global product complaint management system.

Study and Site Closure

Discontinuation of Study Sites

Study site participation may be discontinued if Lilly or its designee, the investigator, or the ERB/IRB of the study site judges it necessary for medical, safety, regulatory, or other reasons consistent with applicable laws, regulations, and GCP.

Discontinuation of the Study

The study will be discontinued if Lilly or its designee judges it necessary for medical, safety, regulatory, or other reasons consistent with applicable laws, regulations, and GCP.

Appendix 3. Clinical Laboratory Tests

Clinical Laboratory Tests

Hematology - central laboratory^a

Leukocytes (WBC)	Erythrocytes (RBC)
Neutrophils ^b	Hemoglobin (HGB)
Lymphocytes	Hematocrit (HCT)
Monocytes	Mean corpuscular volume (MCV)
Eosinophils	Mean corpuscular hemoglobin concentration (MCHC)
Basophils	Platelets (PLT)

Chemistry - central laboratory (except as indicated)^a

Serum Concentrations of:

Alanine aminotransferase (ALT)	Calcium
Albumin	Chloride
Alkaline phosphatase	Creatinine
Aspartate aminotransferase (AST)	Potassium
Bilirubin, direct	Protein, total
Bilirubin, total (TBL)	Sodium
Blood urea nitrogen (BUN) or blood urea	Triglycerides (Arm A only) ^c

Renal panel - central laboratory

Cystatin-C

Pregnancy Test (for female patients of childbearing potential) - local laboratory

Serum pregnancy test^d

Abbreviations: CRF = case report form; RBC = red blood cells; WBC = white blood cells.

- ^a Treatment decisions may be based on local laboratory results.
- ^b Neutrophils reported by automated differential hematology instruments include both segmented and band forms. When a manual differential is needed to report the neutrophils, the segmented and band forms should be reported together.
- ^c Arm A only. Triglycerides will be evaluated every other cycle starting with Cycle 2 until Cycle 6, and then every third cycle thereafter until treatment discontinuation.
- ^d Additional serum pregnancy tests may be performed locally, on Day 1 (or up to 3 days before Day 1) of every cycle beginning with Cycle 2 and at short term follow up for women of child bearing potential if mandated by local country regulations.

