Patient diary dispensing/collection	X	X	X	X	X	Patient diaries should be completed by the patient during cycles 1, 2, and 3.	
Administer mBPI-sf and EORTC QLQ-C30 questionnaires	X	X	X		X	To be administered prior to extensive interaction with site staff at each visit when administered. Continue administration at every cycle through Cycle 7 Day 1 and then administer at every other cycle starting with Cycle 9 and beyond.	
Administer abemaciclib	X						Administer prescribed dose orally every 12 hours on Days 1 through 28 of every cycle. Patients may take study drug with or without meals.

On-Study-Treatment Schedule of Activities

Day within cycle (28 days = 1 cycle)	Cycle 1		Cycle 2		Cycle 3 and beyond (per instructions)	Comments
	1	15	1	15	1	
Procedure						
Administer tamoxifen	X					Arm A patients only. Administer prescribed dose orally every 24 hours on Days 1 through 28 of every cycle.
Administer loperamide	X					Only patients in Arm C should take loperamide prophylactically (daily during Cycle 1 with their first dose of abemaciclib). Patients in Arms A and B should only take loperamide if the patient experiences diarrhea and requires treatment. See Section 7.4.1.1.3 for additional information.
Sample collection						
Central hematology	X	X	X	X	X	Central hematology labs can be drawn up to 3 days prior to Day 1 of each cycle, as well as up to 3 days prior to Day 15 of Cycles 1 and 2. Additional local hematology labs may be drawn for treatment adjustment and patient management purposes. Duplicate central labs should be submitted for assessment. Discrepancies between local and central laboratory results will not be considered protocol deviations.
Central chemistry	X	X	X	X	X	Central chemistry labs can be drawn up to 3 days prior to Day 1 of each cycle, as well as up to 3 days prior to Day 15 of Cycles 1 and 2. Additional local chemistry labs may be drawn for treatment adjustment and patient management purposes. Duplicate central labs should be submitted for assessment. Discrepancies between local and central laboratory results will not be considered protocol deviations.
Serum pregnancy test			X		X	Required only for women of child bearing potential if mandated by local country regulations. Additional serum pregnancy tests performed locally, on Day 1 (or up to 3 days before Day 1) of every cycle beginning with Cycle 2.
Pharmacokinetics	X	X	X	X	X	See Appendix 4 for details on sample collection
Pharmacogenetic blood sample	X					

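### Arm A triglycerides have no scheduled pre-treatment value, so for this one test a change from the pre-treatment state cannot be derived from scheduled data

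*Protocol*

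**What the plan says.** Appendix 3 lists triglycerides in the central chemistry panel, restricted to Arm A. Footnote c sets the timing: "Triglycerides will be evaluated every other cycle starting with Cycle 2 until Cycle 6", "and then every third cycle thereafter until treatment discontinuation". No other section of the protocol mentions the test.

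Section 10.3.2 lists the safety summaries to be produced by arm in the safety population. One of them is "treatment-emergent abnormal changes in laboratory values", with no test excepted.

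The protocol does not define treatment-emergent for laboratory values. Appendix 1 defines it for adverse events, as an occurrence "having been absent pretreatment, or worsens relative to the pretreatment state".

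Table JPCG.2 starts abemaciclib and tamoxifen on Cycle 1 Day 1. For tamoxifen the instruction is "Administer prescribed dose orally every 24 hours on Days 1 through 28 of every cycle", and the table header gives "28 days = 1 cycle".

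**The concern.** A treatment-emergent change compares an on-treatment value with the state before treatment. Footnote c begins triglyceride sampling one cycle after dosing has begun, so the reference half of that comparison is never collected under the protocol. The other arms cannot supply a reference, because the test is not done there.

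What is at stake is whether a raised triglyceride value in Arm A can be classed as new. Nothing in eligibility limits the starting level: the organ-function criteria in Section 6.1 contain no triglyceride limit. Some patients may therefore enter with raised values, and the schedule would not show which. Once dosing has begun, the missing value cannot be recovered.

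**Working it through.** There is no sample-size, power or event figure to reproduce. The check is a count of scheduled samples and days, followed by a comparison of the sections.

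**1. Scheduled cycles (Appendix 3, footnote c).** Every other cycle from 2 to 6 gives Cycles 2, 4 and 6. Every third cycle after that gives 6 + 3 = 9, 9 + 3 = 12, and so on. Cycle 1 and the baseline period do not appear.

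**2. Earliest possible scheduled value (Table JPCG.2).** The cycle length is 28 days, and "Central chemistry labs can be drawn up to 3 days prior to Day 1 of each cycle".

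| Draw | Study day | Dosing days completed before it |
|---|---|---|
| Cycle 2 Day 1, 3 days early | 29 − 3 = 26 | 25 |
| Cycle 2 Day 1 | 28 + 1 = 29 | 28 |
| Cycle 2 Day 15 | 28 + 15 = 43 | 42 |

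Footnote c names the cycle but not the day, and Cycle 2 has chemistry draws on both Day 1 and Day 15. The earliest reading is therefore about 25 to 28 days of treatment. These counts assume no cycle delay or dose suspension.

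**3. Patients with a scheduled pre-treatment value.** Section 10.1 plans 225 patients in three equal arms: 225 / 3 = 75 in Arm A. The number with a scheduled pre-treatment triglyceride value is 0 of about 75.

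**4. Does the general chemistry panel fill the gap?** Table JPCG.1 takes central chemistry within 14 days before Day 1, and Table JPCG.2 takes it again on Cycle 1 Day 1. Neither supplies the value as written:

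- The screening sample supports enrollment, and under Section 7.2 randomization follows once all criteria are met. The arm is therefore normally unknown at that draw, and a test restricted to Arm A cannot be selected for it.
- The Cycle 1 Day 1 sample could carry the test, but footnote c, which is specific to triglycerides, starts a cycle later.

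**5. Can an analysis rule repair it?** The possible conventions for a missing reference value have these consequences:

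| Convention | Consequence for triglycerides |
|---|---|
| Treat the missing baseline as normal | A pre-existing elevation is counted as emergent |
| Exclude patients without a baseline | Based on scheduled data, 0 patients remain in the summary |
| Use Cycle 2 as the reference | Any change during the first cycle is hidden |
| Report on-treatment values only | Valid, but no longer a treatment-emergent summary |

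Only the last is free of misclassification, and it amounts to the exemption that Section 10.3.2 does not make.

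**The case against.** Several points on the other side have force.

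- **The laboratory rule belongs in the SAP.** The protocol defines treatment-emergent only for adverse events, and the handling of a missing baseline is ordinary SAP content. This stands as far as the rule goes, and it means that no one can say from the protocol alone whether pre-existing elevations would be over-counted or real rises missed. It does not dispose of the point, because the sampling schedule is protocol content and a SAP cannot supply a value that was never drawn.
- **The values remain useful.** Results at Cycles 2, 4, 6, 9, 12 and so on show an on-treatment trend within each patient and can be graded against the normal range. Table JPCG.1 also records medical history, current medications and graded pre-existing conditions, so known hypertriglyceridemia or lipid-lowering treatment should be visible. This stands. A reader might infer that the triglyceride data are uninterpretable or that nothing can be reported, and the document does not support that. What is lost is the comparison with the pre-treatment state.
- **The purpose of the test is not stated.** A reader might infer that it was included to detect a safety signal of the combination, so that its absence from Arms B and C is itself a defect. The protocol gives no such rationale. Section 9.4.1 says that blood samples serve eligibility and patient monitoring, and no objective or endpoint names triglycerides. A sparse schedule in one arm fits individual monitoring equally well, so the restriction to Arm A is not criticized here.
- **A Cycle 1 Day 1 sample is not automatically pre-treatment.** Table JPCG.2 permits the draw on Day 1 or up to 3 days earlier, but does not require it before the first dose. Appendix 4 does require this for the biomarker plasma sample. This stands, and any correction has to state it.

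**Conclusion.** The point holds in a limited form. Footnote c schedules no pre-treatment triglyceride value for any of the roughly 75 Arm A patients, and the first planned value follows about 25 to 28 days of treatment. Section 10.3.2 promises treatment-emergent laboratory changes without exempting this test. From scheduled data, that summary cannot separate a new elevation from a pre-existing one.

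This rests on two assumptions: that sites follow footnote c and do not draw triglycerides earlier on their own initiative, and that treatment-emergent carries for laboratory values the meaning that Appendix 1 gives it for adverse events.

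The size is minor. It concerns one safety analyte in one arm. It does not touch PFS, the other efficacy endpoints, power or the other laboratory tests.

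**What to change.** In Appendix 3, footnote c, add triglycerides for Arm A to the existing Cycle 1 Day 1 central chemistry sample, and state that this sample is drawn before the first dose of study treatment.

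For patients already enrolled without that value, or if the sponsor prefers to leave sampling unchanged, state that triglycerides are reported as on-treatment values only and are excluded from the treatment-emergent summary in Section 10.3.2.

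The cost is one extra analyte on a sample that is already taken, for about 75 patients, with no added visit or blood draw. The change cannot restore a pre-treatment value for patients who have already started treatment.
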